### 4.3 Other study variables

The following endpoints will be noted, as copeptin results may differ when stratified according to:

- Weight
- Sex
- Postnatal days and postconceptional age in neonates
- Exogenous vasopressin administration

## 5. PROJECT DESIGN

### 5.1 Type of research and general project design

The proposed study is designed as a single-centre prospective observational study.

This design was chosen to gather data on all or at least on a large fraction of critically ill children and neonates admitted to our intensive care unit, assuming patients' or care takers informed consent. Further, as data on copeptin in critical ill children is scarce, no randomization or intervention other than taking blood samples will be necessary. Limitation: The observational study design will not be able to answer any kind of causative questions related to study findings.

### 5.2 Procedures

As soon as written informed consent is obtained from care takers, the study period will begin for the included children and neonates. The primary study period is defined as 48 hours. For all patients discharged from the ICU within 48 hours after admission, the study period will end with discharge from ICU. 62.3 % of patients stay less than 48h in the ICU of the University Children's Hospital Zurich (median (10th- 90th percentile): 1.3 (0.4-9.2) days). The sample size was calculated to compensate for these patients discharged early. Patients staying longer than 48 hours (37.7%) are generally those patients with a higher degree of disease severity and are of specific interest. For all patients staying longer than 48 hours, the study period will end with discharge from ICU or with 168 hours, whichever comes first,

On admission demographic baseline data will be recorded on paper bedside case report forms as outlined in "Schedule of assessment (Flow of research project)" (i.e. age (years + months; if <28 days: postnatal days and postconceptional age), Apgar-score, arterial umbilical cord pH; diagnosis; disease-severity-scores; operation, preoperative parameters; weight; sex). Blood samples (600 µl) will be taken from all study patients on specific points of time (on admission, with 12, 24, 48, and, if still in ICU with 96, and 168 hours following admission), processed and stored at -80 °C for batch analyses later. Just before or after blood sampling the following clinical data will be recorded: arterial blood pressure; vital parameters (respiratory rate, peripheral oxygen saturation, arterial oxygen saturation, perfusion index, heart rate, peripheral pulses, capillary refill, urine output); laboratory values (sodium, potassium, calcium, chloride, troponin, creatine kinase, creatine kinase MB, pH, partial arterial oxygen pressure (PaO2), partial carbon arterial carbon dioxide pressure (PaCO2), base deficit, arterial lactate, glucose, alanine transaminase (ALT), creatinine, C-reactive protein, haemoglobin, white blood cell count, total bilirubin); neurological parameters (Glasgow Coma Scale, CT-findings (abnormal cisterns, midline shift >5mm, traumatic subarachnoidal haemorrhage, seizures, intracranial and cerebral perfusion pressure (if invasively monitored)); neonatal parameters (results of neonatal neurological imaging (cranial ultrasound and/or MRI) and performance of neonatal cooling as prevention of neurological damage). Importantly, laboratory parameters will only be assessed, if their analysis is otherwise medically indicated for limitation of blood loss and phlebotomy. As most critically ill patients have to be equipped with invasive hemodynamic monitoring allowing repetitive blood withdrawal, no additional phlebotomy should be necessary. Copeptin values will only be analysed, when the study blood sample can be taken alongside with other medically indicated blood samples.

If the study patient is discharged from the ICU, the study period ends and no further blood samples or clinical data will be taken or analysed. Length of ICU stay will be noted. Every patient will be followed by study investigators for a total of 28 days to note date of discharge from ICU, Hospital and date of death, if applicable.

As outlined in 2.4 "Participant Information and Informed Consent" this study may include patients, who themselves or whose caretakers may not be able to give written informed consent in emergency situations due to acute clinical deterioration, resuscitation and/or sedation of the patients. Further, care takers may not be present or accountable for formal medical explanations and may not be able to give informed consent at the time of intensive care unit admission due to the deterioration of their child.

In this case, blood samples for copeptin will be taken, but not analysed. As soon as possible, but latest 24 hours following intensive care unit admission, written informed consent will be obtained. If no informed consent can be obtained within 24 h after ICU-admission, all blood samples will be destroyed and the patient will be excluded.

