### 2.4 Participant Information and Informed Consent

All patient care takers and adolescents (if age  $\geq 14$  years) have to give written informed consent. Informed consent forms will be only available in German. For enrolment, patients, parents, family members or other care takers must have sufficient knowledge of German to understand the instructions, given by their treating intensive care specialist. Written informed consent for study inclusion should be obtained from patients (if  $\geq 14$  years of age), patients' parents or care takers before first study relevant blood sample is taken and before first patient data are recorded.

In this study we have to include vulnerable patients, please see chapter 3.3 risk-benefit assessment.

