This study may include patients, who themselves or whose caretakers may not be able to give written informed consent in emergency situations. This may be due to acute clinical deterioration, resuscitation and/or sedation of the patients. Further, care takers may not be present or accountable for formal medical explanations and may not be able to give informed consent at the time of intensive care unit admission due to the deterioration of their child. In this case, blood samples for copeptin will be taken, but not analyzed. As soon as possible, but latest 24 hours following intensive care unit admission, written informed consent will be obtained from care takers, if patient  $< 14$  years or if patient  $\geq 14$  years and sedated for more than 24 hours. If the adolescent ( $\geq 14$  years of age) stays sedated or unable to give informed consent for more than 24 hours, the presumptive will of the adolescent has to be taken into account by the legal care takers when giving informed consent in her/his place. Written informed consent will be obtained from the patient her-/himself, if  $\geq 14$  years and sedated for less than 24 hours in agreement with HFG Art. 30, Abs. 2. If a legal care taker gives informed consent in place of an adolescent ( $\geq 14$  years of age), the informed consent must be obtained from the adolescent her-/himself as soon as the adolescent is able to give consent her-/himself. If the adolescent is not willed to give consent, all data and blood products obtained until then will be destroyed in this case. The volume of blood necessary for the copeptin analysis (600  $\mu$ l each sample) is not relevant for any age group including neonates. The additional clinical data needed for primary and secondary endpoint assessment is open-label. Study relevant data is available in medical files and electronic patient data management systems of the intensive care ward anyway. In addition, copeptin analyses will be performed only for blood samples from patients with written informed consent using a pooled batch of blood samples several weeks later.

In case written informed consent cannot be obtained within 24 hours after admission, the patient will not be included in the study, all blood samples will be destroyed and no patient data will be analyzed (in agreement with HFG Art. 31 Abs.1+2).

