## **4. OBJECTIVES, ENPOINTS/OUTCOMES AND OTHER STUDY VARIABLES**

### **4.1 Objectives**

#### **Primary objective**

The primary objective is to investigate the average change of blood copeptin levels in critically ill children and neonates with both arterial normo- and hypotension over 48h after intensive care unit (ICU) admission, and in a second step to describe the natural course and variability of copeptin levels over a period of up to 7 days after ICU admission. In this scope we will also investigate the association of patient characteristics (covariates) with blood copeptin baseline levels at ICU admission and the course of blood copeptin levels during ICU stay. In particular the association with the following factors will be investigated:

- Arterial blood pressure (in particular hypotension vs. normotension), to identify patients that may most benefit from exogenous AVP treatment
- Septic shock
- Heart failure
- Traumatic head injury, brain tumor and/or intracranial operation
- Perinatal asphyxia
- Severity of disease (disease score)
- Age

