### **5.3 Recruitment and Screening**

All care takers of eligible critically ill children or neonates admitted to the intensive care unit of the University's Children Hospital Zurich will be consecutively assessed during daily clinical routine by study investigators. One hundred and seventy study patients are targeted and should be enrolled within 18 months, as a total of 1800 children and adolescents are admitted to the department of Intensive Care Medicine and Neonatology at the University's Children Hospital Zurich.

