## 8. STATISTICAL METHODOLOGY

### 8.1 Determination of Sample Size

The sample size calculation is based on the primary objective, namely to investigate the average change of blood copeptin levels (mean difference between time-points, i.e. from admission to 12h, from 12h to 24h, from 24h to 48h) in critically ill children and neonates with both arterial normo- and hypotension over 48h after ICU admission.

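### Protocol 5.2 starts the study period at consent while the endpoint runs from ICU admission, and the consent rules let the delay of the nominal admission sample depend on the child's condition

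*Protocol*

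**What the plan says.** **Time origin.** Protocol 5.2 ties the start of the study to consent: "As soon as written informed consent is obtained from care takers, the study period will begin for the included children and neonates". It then gives a length with no origin: "The primary study period is defined as 48 hours". The next sentence counts from admission: "For all patients discharged from the ICU within 48 hours after admission, the study period will end with discharge from ICU". Section 4.1 sets the primary objective "over 48h after intensive care unit (ICU) admission", and 8.1 bases the sample size on change in "critically ill children and neonates with both arterial normo- and hypotension over 48h after ICU admission". The sampling times in 4.2, in 5.2 and in the Schedule of Assessments also run from ICU admission.

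**Consent order.** Under 2.4, written consent should come "before first study relevant blood sample is taken and before first patient data are recorded". The exception covers emergencies in which consent cannot be given: acute deterioration, resuscitation or sedation of the child, or carers who are absent or unable to consent. There, "In this case, blood samples for copeptin will be taken, but not analyzed", and consent must follow within 24 hours of admission. Section 5.2 repeats this exception.

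**Approach to families.** Section 5.3 says that carers of admitted children are "consecutively assessed during daily clinical routine by study investigators".

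**Use of the value.** Section 8.2.1 tests the admission-12 h, 12-24 h and 24-48 h changes by two-sided t-test. It also models covariate effects on baseline and course. Section 5.4 concludes that bias has no notable way into this study.

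**The concern.** Two clocks are in use. A site reading the opening of 5.2 could start the 48-hour period at the signature; every endpoint definition starts it at ICU admission.

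The consent rules add a second issue. A child whose condition prevents consent may be sampled at once and the sample held. A child whose carers can consent should not be sampled until they sign. Both then contribute to the time point called admission, and no limit is set on how late that draw may be. The Schedule of Assessments marks only the 12 to 168 h draws as flexible.

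Two results depend on this draw. It is the first term of the admission-12 h t-test. It is also the baseline level whose association with blood pressure, hypotension against normotension in particular, belongs to the primary objective (4.1). Under 6.1 the children with normal pressure supply the reference values. Since 8.1 hypothesises that copeptin changes between time points, a delay related to illness could be mistaken for an effect of blood pressure on baseline.

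**Working it through.** **1. The plan's own figure.** Section 8.1 takes d = 0.3 ng/mL and sd = 0.75 × 1.1 = 0.825 ng/mL, so d/sd = 0.3636. A two-sided one-sample t-test on within-child change at 5% gives n = 62 for 80% power, as in Table 3. Then 62 × 2.5 × 1.1 = 170.5, stated as 170. The figure reproduces and is not in dispute. It shows that the test is on change between two draws in the same child, so the timing of both draws matters.

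**2. Time zero, place by place.**

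| Place | Counted from |
|---|---|
| 5.2, start of study period | consent |
| 5.2, length of primary period | not stated |
| 5.2, early-discharge rule | ICU admission |
| 4.1, primary objective | ICU admission |
| 4.2, 5.2 and Schedule, sampling times | ICU admission |
| 8.1, sample-size basis | ICU admission |

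Only the start of the study period is tied to consent. Consent may come up to 24 h after admission, which is 24/48 = half of the primary period.

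**3. Who may be sampled before consent.** The default is consent first. The exception is inability to consent, for reasons mostly connected with the child's condition. The rules thus open a path from illness to sampling delay. They do not show how long any delay is.

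**4. Effect on the first interval.** If the first draw is h hours late, the nominal 12 h interval is really 12 - h hours: 10 h for h = 2, 6 h for h = 6, nothing for h = 12.

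**5. Illustration of size.** Assumptions, none of them from the protocol: the planned 0.3 ng/mL change is linear over 48 h (0.3/48 = 0.00625 ng/mL per hour), the SD is unchanged, and a share s = 50% of children have a first draw h hours late.

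- Baseline shift in a late child = 0.00625 × h, compared with SD 0.82.
- Mean admission-12 h change = 0.075 × (1 - s × h/12), where 0.075 = 0.00625 × 12.
- Power for the admission-48 h change, n = 62: effect 0.36 × (1 - s × h/48).

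| h | Baseline shift (ng/mL) | Shift / SD | Mean admission-12 h change (ng/mL) | Power, admission-48 h |
|---|---|---|---|---|
| 0 | 0 | 0 | 0.075 | 0.797 |
| 2 | 0.0125 | 0.015 | 0.069 | 0.780 |
| 6 | 0.0375 | 0.046 | 0.056 | 0.744 |
| 12 | 0.075 | 0.091 | 0.0375 | 0.685 |
| 24 | 0.150 | 0.183 | not defined | 0.553 |

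The power at h = 0 is 0.797 because the rounded effect 0.36 is used. The row for 24 h is the outer limit set by the consent deadline, not an expected delay. The power column applies to the change from admission to 48 h described in the synopsis; among the successive-interval tests in 8.2.1, only the first uses the admission draw.

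Table 2 of the protocol has a single row for 0-24 h, from 13 children with septic shock. It gives no information on how copeptin moves within the disputed hours.

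**The case against.** The strongest reply is that the protocol anchors every sampling time and every test to ICU admission. On that reading a child not sampled at admission simply has no admission value, and one clarifying sentence repairs 5.2. Consent can be obtained promptly, which would give a stable child a true admission sample. Emergency draws must still coincide with medically indicated blood sampling, so they are not guaranteed on arrival either. The mixed model handles unbalanced data and can use actual times.

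Much of this stands, and it limits the point. Several stronger readings are not supported:

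- **Baseline timing in fact differs by severity.** The rules permit this, but no consent delays are given.
- **Hypotensive children are sampled early and normotensive children late.** The trigger is inability to consent, not blood pressure. A sedated normotensive child may take the exception; a hypotensive child whose carer can sign takes the default.
- **The window could run to 72 h (24 + 48).** This needs the opening of 5.2 read apart from its own discharge rule and from 4.1.
- **The t-test could produce a blood-pressure difference.** It pools all included patients and compares no groups. It can be diluted, but it cannot generate that contrast.
- **Waiting for consent loses many short-stay children.** The stay figures in 5.2 (median 1.3 days, 10th percentile 0.4 days) describe length of stay, not time to consent.

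The reply does not remove three things: 5.2 conflicts with itself; the admission draw has no stated time limit; and the model can use actual times only if they are recorded, while the clock time of the draw is not among the items listed in the Schedule of Assessments or 5.2.

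**Conclusion.** The point holds in a limited form. The protocol uses two time origins that must be reconciled, and its consent rules allow the delay of the nominal admission sample to depend on the child's condition. Two analyses are exposed: the admission-12 h t-test, through a shortened interval, and the baseline comparison of hypotensive with normotensive children, through confounding by sampling delay. The statement in 5.4 is therefore too absolute.

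The size cannot be established from the document. Under the linear illustration a delay of 2 h is minor for both analyses. At 6 h in half of the children, the mean first-interval change falls by a quarter (0.075 to 0.056 ng/mL), while the baseline shift stays under 0.05 SD. Larger effects need longer delays or faster early change in copeptin, and the protocol documents neither. The sample size of 170 is unaffected.

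**What to change.** - In 5.2, make ICU admission time zero for the study period, the 48-hour primary period and all nominal draws, whatever the time of consent.
- Record on the case report form the actual time of consent and of each copeptin draw.
- Count a draw as the admission sample only if it falls within an early window after ICU admission, fixed in advance. Leave a later first draw out of the admission-12 h t-test and enter it in the mixed model at its actual time.
- Report the delay to first sample by blood-pressure group.
- Revise 5.4 to name sampling delay as a possible source of bias and to refer to these measures.

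The cost is protocol wording, one or two form fields, and the loss of some late first samples from the first t-test. The times should be collected prospectively, since they may be hard to recover later. The rule on who may be sampled before consent need not change; widening it would be an ethics decision and is not proposed here.

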### **5.3 Recruitment and Screening**

All care takers of eligible critically ill children or neonates admitted to the intensive care unit of the University's Children Hospital Zurich will be consecutively assessed during daily clinical routine by study investigators. One hundred and seventy study patients are targeted and should be enrolled within 18 months, as a total of 1800 children and adolescents are admitted to the department of Intensive Care Medicine and Neonatology at the University's Children Hospital Zurich.

### **5.4 Methods of minimising bias**

This is an observational study comparing blood values to clinical conditions. As blood values have to be obtained via one of the procedures most routinely used in the intensive care setting (i.e. venous, arterial or capillary blood sampling), no relevant bias is expected to influence this point. All clinical parameters will be available open-label to treating physicians and study personal in medical charts, no bias is expected here either. Treating physicians will be blinded to copeptin values. Staff analysing copeptin levels at the BRAHMS laboratory will be blinded to clinical course of the patient.

Taken together, no special bias entry points are relevant to this study.

## **6. PROJECT POPULATION**

### **6.1 Inclusion criteria**

This is a study designed to explore Copeptin values in all kinds of critically ill paediatric patients. Patients with normal blood pressures will allow calculating Copeptin reference values for the ones requiring cardiovascular support. Therefore, all patients, irrespective of their medical condition (e.g. medical or surgical, mildly or severely affected) and their age (neonates to adolescents) admitted to the Intensive Care Unit of the University's Children Hospital Zurich will be eligible, as long as they fulfil the following conditions:

- Age: first day of life until 18th birthday.
- Ability of the care taker or the adolescent (if  $\geq 14$  years of age) to understand verbal and written instructions and informed consent in German.

### **6.2 Exclusion criteria**

Patients will not be included in the study for the following reasons:

- Care taker or adolescent (if  $\geq 14$  years of age) unwilling to give written informed consent.
- Care taker or adolescent (if  $\geq 14$  years of age) not understanding German and without a family member able to translate.
- Adolescent (if  $\geq 14$  years of age) unwilling to give written informed consent following sedation  $< 24$  hours.
- Care takers of long-term sedated ( $> 24$  hours) adolescents (if  $\geq 14$  years of age) unwilling to give written informed consent or not present within 24 hours.

### **6.3 Criteria for withdrawal / discontinuation of participants**

For the following reasons the study period will end immediately for the included patients.

- Withdrawal of informed consent
- Discharge from Intensive Care Unit
- Death

## **7. PROJECT ASSESSMENTS**

### **7.1 Project flow chart(s) / table of procedures and assessments**

Please see study flow chart under "SCHEDULE OF ASSESSMENTS (FLOW OF RESEARCH PROJECT)", page 8.

### **7.2 Assessments of primary endpoint/outcome**

The following primary endpoint variable will be obtained in laboratory analysis and stored in an electronic database:

- Blood copeptin values. All study blood samples will be sent labelled with patients' names and study numbers to the internal laboratory of the University Children's Hospital Zurich for centrifugation, aliquot preparation and storage. The stored aliquots assigned to copeptin analysis will be sent in batches to

BRAHMS (Thermo Fisher Scientific) in Hennigsdorf, Germany. Before the aliquots leave the Children's Hospital Zurich, all aliquots will be re-labelled manually by study staff to be coded with study number only. All results will be received from BRAHMS in a coded form and stored in a coded database inside the University Children's Hospital Zurich.

The following primary endpoint variables will be obtained and noted on bedside paper case report forms:

- Arterial blood pressure: obtained via invasive (indwelling peripheral or central arterial catheters) or non-invasive (oscillometric or auscultatory) measurements.
- Diagnosis.
- Vital parameters: respiratory rate, peripheral oxygen saturation, arterial oxygen saturation, perfusion index, heart rate, peripheral pulses, capillary refill, urine output.
- Laboratory values: sodium, potassium, calcium, chloride, troponin, creatine kinase, creatine kinase MB, pH, partial arterial oxygen pressure ( $\text{PaO}_2$ ), partial carbon arterial carbon dioxide pressure ( $\text{PaCO}_2$ ), base deficit, arterial lactate, glucose, alanine transaminase (ALT), creatinine, C-reactive protein, haemoglobin, white blood cell count, total bilirubin; all if medically indicated.
- Fluid administration/24h each day.
- Operation and perioperative parameters, i.e. preoperative medication, anaesthetics, type of surgery; if cardiac surgery in addition: cardiac lesion, echocardiographic and cardiac catheter results, periods of cardiopulmonary bypass, cross clamping, deep hypothermic arrest, modified ultrafiltration, postoperative echocardiographic results.
- Neurological findings: Glasgow Coma Scale, CT-results (abnormal cisterns, midline shift  $>5\text{mm}$ , traumatic subarachnoidal haemorrhage, seizures, intracranial and cerebral perfusion pressure (if invasively monitored)).
- Neonatal findings: Apgar-score, arterial umbilical cord pH, results of neurological imaging (cranial ultrasound and/or MRI), and performance of neonatal cooling as prevention of neurological damage.
- Organ dysfunction/mechanical resuscitation.
- Disease-Severity-Scores (PIM 2, SAPS II, CRIB II).

